Subjects will be classified as adrenally sufficient or insufficient on the basis of standard-dose cortisol stimulation test. Variables of interest for comparison between the groups include MELD score, Child-Turcotte-Pugh (CTP) classification, high-density lipoprotein (HDL) levels, presence of spur cell anemia, serum cholesterol ester percentage (surrogate for LCAT enzymatic activity), cortisol binding globulin levels, and free cortisol levels. Student's t-test and Chi Square tests will be utilized to determine significance; a p-value <0.05 will be used as our threshold for significance. If multiple factors are found to be significantly different in a univariate fashion between classification groups, a multivariate logistic regression analysis will be performed for adjusted analysis. We will also seek to define any correlations between variables. Furthermore, we will assess correlation between MELD score and serum cholesterol ester percentage, spur cell anemia, HDL levels, cortisol binding globulin levels, and free cortisol levels; similar correlate analysis will be done using CTP classification instead of MELD score.

Prevalence of adrenal insufficiency (AI) in cirrhosis varies widely based on several factors, including severity of liver disease (i.e. MELD score or CTP classification) and the testing modality used to assess for AI. Given that admitted patients to UVA are typically CTP B or C, we expect the incidence to be about 33%. Thus, 120 patients recruited should be sufficient to provide a statistical difference in our outcome measures of interest, assuming a 20% dropout rate to lead to 100 patients completing study protocol.

3. Provide a justification for the sample size used in this protocol.

Answer/Response:

Given that admitted patients to UVA are typically CTP B or C, we expect the incidence of adrenal insufficiency to be about 33%. We feel 100 patients would be adequate to complete a pilot study to test for correlation between adrenal insufficiency, low serum cholesterol ester percentage, and spur cell anemia. There is no current literature upon which to do a formal power calculation (although low levels of cholesterol esterification is a well-established near-universal metabolic finding in cirrhotic patients), but this sample size would allow for adequate size comparator groups and decrease the likelihood of a Type II statistical error.

4. What is your plan for primary variable analysis?

Answer/Response:

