Our primary outcome of interest is comparing prevalence of cholesterol esterification deficiency and spur cell anemia in cirrhotic patients with and without adrenal insufficiency.

5. What is your plan for secondary variable analysis?

Answer/Response:

- Demonstrate association between deficiency in cholesterol esterification and presence of spur cell anemia

- Demonstrate association between deficiency in cholesterol esterification and low HDL levels
- Correlate higher MELD score with presence of adrenal insufficiency
- Correlate higher MELD score with presence of spur cell anemia
- Correlate higher MELD score with lower HDL levels
- Correlate higher MELD score with deficiency in cholesterol esterification
- Correlate higher CTP classification with presence of adrenal insufficiency
- Correlate higher CTP classification with presence of spur cell anemia
- Correlate higher CTP classification with lower HDL levels
- Correlate higher CTP classification with deficiency in cholesterol esterification
- Correlate lower cortisol binding globulin levels with higher MELD score and CTP classification
- Correlate lower cortisol binding globulin levels with adrenal insufficiency
- Correlate lower free cortisol levels with higher MELD score and CTP classification
- Correlate lower free cortisol levels with adrenal insufficiency
- Multivariate logistic regression if several variables are found to be significant

6. Have you been working with a statistician in designing this protocol?

Answer/Response: No

IF YES, what is their name?

Answer/Response: N/A

7. Will data from multiple sites be combined during analysis?

Answer/Response: No

7(a). Does the study involve randomization?

Answer/Response: No

IF YES, will randomization be done at each site or among sites?

Answer/Response: N/A

7(b). Has the sample size calculation considered the variation among sites?

Answer/Response: N/A

7(c). When combining the data from multiple sites to assess the study results, is the effect of the treatment to be tested (or the association to be tested) assumed to be the same across sites or vary among sites? What is the modelling strategy?

Answer/Response: N/A

7(d). Is there a common protocol used in all sites?

Answer/Response: N/A

IF NO, how will differences among sites, such as those related to the implementation, inclusion criteria, patient characteristics, or other sites characteristics, be considered to assess the study results?

Answer/Response: N/A

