Study Procedures-Biomedical Research

1. What will be done in this protocol?

Answer/Response:

Hospitalized cirrhotic patients at UVA that meet study eligibility criteria will be approached by a member of the study team to obtain consent for participation. If a patient agrees to become a study subject, women of childbearing potential will be administered a urine pregnancy test to exclude pregnancy. Eligible subjects will have an approximate total of 35ml of blood drawn by the inpatient phlebotomy team. Lab tests to be performed include: peripheral blood smear, lipid panel, free cortisol, cortisol binding globulin, serum cholesterol esters (surrogate for LCAT enzyme activity), and a standard-dose cortisol stimulation test. The latter involves blood drawn with the initial collection, administration of an intravenous 250mcg dose of synthetic ACTH by the patient's nurse, and then repeat small-volume (2 teaspoons) blood draws at 30 minutes and 60 minutes later.

The interventions listed above have the potential to identify subjects with adrenal insufficiency, which may be beneficial to their long-term care. Early identification of adrenal insufficiency may lead to earlier corticosteroid administration in critical illness or GI bleeding, thus improving morbidity and mortality. Otherwise, the blood draws themselves pose minimal risk given that it is a routine procedure done during hospitalization, often on a daily or even more frequent basis. Very small risks of bleeding, bruising, or infection do exist.

Most patients tolerate intravenous ACTH as part of the cortisol stimulation test, however known reactions include nausea, diaphoresis, dizziness, pruritus, palpitations, and facial flushing. All patients will be monitored and these side effects, if present, typically resolve within a few hours. Any patients identified as having adrenal insufficiency will be reported to the primary hepatology team caring for the patient to determine whether or not endocrinology consult and/or treatment should be considered.

2. If this protocol involves study treatment, explain how a subject will be transitioned from study treatment when they have completed their participation in the study.

Answer/Response: N/A

Subject Compliance with Study Procedures

1. Explain how the study team will monitor the subject for compliance with the study procedures.

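### Time of day of the cortisol draw is neither fixed nor analysed, so any spread in draw times weakens the two free-cortisol secondary objectives

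*Combined protocol and SAP*

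**What the plan says.** Study Procedures-Biomedical Research, item 1, describes the sampling. "Eligible subjects will have an approximate total of 35ml of blood drawn by the inpatient phlebotomy team", and "Lab tests to be performed include: peripheral blood smear, lipid panel, free cortisol, cortisol binding globulin", followed by cholesterol esters and the stimulation test. The pre-ACTH cortisol sample is tied to the first draw: "The latter involves blood drawn with the initial collection". The later samples are timed only relative to ACTH: "blood draws at 30 minutes and 60 minutes later". No clock hour or window is given for the first draw.

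Statistical Considerations, item 5, lists two secondary objectives that use free cortisol: "Correlate lower free cortisol levels with higher MELD score and CTP classification" and "Correlate lower free cortisol levels with adrenal insufficiency". Item 2 plans t-tests, chi-square tests and correlations. It adds a multivariable step that depends on the univariate results: "If multiple factors are found to be significantly different in a univariate fashion between classification groups, a multivariate logistic regression analysis will be performed". Time of day is not among the variables listed.

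On the AI label, item 2 says: "Subjects will be classified as adrenally sufficient or insufficient on the basis of standard-dose cortisol stimulation test". No cut-off is given, and the plan does not say whether baseline, peak or increment decides the class.

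**The concern.** Cortisol is generally understood to vary over the day. The documents do not discuss this, so it enters here as ordinary physiology and its size in this population is unknown. Each patient contributes one free-cortisol value. If patients are drawn at different hours, part of the spread between them reflects the clock rather than the patient, and without a time term the two cannot be told apart.

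The direct stake is the two free-cortisol objectives, which would be harder to show. The plan offers no formal power calculation and relies on its 100 completers to limit Type II error, so avoidable noise works against its own argument. Free cortisol could also carry the noise into the conditional logistic model.

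The plan already controls one influence on cortisol by excluding patients with prednisone or hydrocortisone use in the previous 24 hours (Inclusion/Exclusion Criteria, item 2). Draw time is another influence, and it is left open.

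**Working it through.** **Is draw time controlled anywhere?** Setting the sections side by side:

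- Study Procedures, item 1: the first draw has no hour, and later draws are timed relative to ACTH.
- Statistical Considerations, items 2, 4 and 5: no time variable.
- Subject Compliance, item 1: the electronic record can be used to confirm that the draws and the test took place, but no use of the times is planned.

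Draw time is therefore neither fixed nor analysed.

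**Inputs.** From the documents: 100 completers, about 33% with AI (so about 33 against 67), and significance at 0.05, taken as two-sided because sidedness is not stated. The plan gives no power, correlation, effect size or variance for free cortisol, so there is no figure to reproduce. Assumed for illustration: a true correlation of 0.30 (absolute value), a true standardised difference of 0.60, and *k*, the ratio of clock-time variance to between-patient variance.

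**Noise only (draw time unrelated to MELD, CTP or AI).** The clock-time share of total variance is f = k/(1+k), and the attenuation factor is √(1−f) = 1/√(1+k).

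- k = 0.25: 1/√1.25 = 0.89
- k = 0.5: 1/√1.5 = 0.82
- k = 1.0: 1/√2 = 0.71

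Power for a correlation by Fisher's z is Φ(atanh(r_obs)·√97 − 1.96). The sample size for 80% power is ((1.96 + 0.84)/atanh(r_obs))² + 3, with unrounded normal quantiles, rounded up.

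| k | f | Factor | 0.30 observed as | Power, n = 100 | n for 80% power |
|---|---|---|---|---|---|
| 0 | 0 | 1.00 | 0.30 | 86% | 85 |
| 0.11 | 0.10 | 0.95 | 0.285 | 82% | 95 |
| 0.25 | 0.20 | 0.89 | 0.27 | 77% | 107 |
| 0.5 | 0.33 | 0.82 | 0.24 | 69% | 129 |
| 1.0 | 0.50 | 0.71 | 0.21 | 56% | 173 |

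For AI against no AI, the standard error of the standardised difference is √(1/33 + 1/67) = 0.213, and power is Φ(d_obs/0.213 − 1.96). A true difference of 0.60 gives 80% power with no clock-time variance. At k = 0.25 it is observed as 0.54 (71%), and at k = 1.0 as 0.42 (51%). This treats the AI label as free of clock-time error.

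**Bias.** If ρ is the correlation between severity and the clock-time component of free cortisol, the observed correlation is (r + ρ√k)/√(1+k). With ρ = 0 this reduces to the attenuation above. With ρ not zero, the result can move in either direction. The documents give no value or sign for ρ.

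**AI label.** A rule based on baseline cortisol or on the increment would carry draw time into the label, and so into the primary comparison. Free cortisol from the same draw would then share error with the label, and the direction of that association could not be predicted. A rule based only on the stimulated value does not use the baseline sample.

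**Cost of adjusting.** Two time terms change √97 to √95. With r = 0.30 and the clock-time variance fully removed, power is Φ(0.3095 × 9.747 − 1.96) = Φ(1.057), about 85%, against 86% with no clock-time variance at all.

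**The case against.** The strongest reply is that the documents are silent on the hour, and silence does not show a spread. The inpatient phlebotomy team might draw most samples at similar times, and with no spread there is no attenuation. Even with a spread, the size is wholly assumed. Only inpatients are enrolled, and their daily rhythm may be blunted; at a 10% clock-time share, power for a correlation of 0.30 falls only from 86% to 82%. The reach is also narrow: two of the fourteen association bullets in item 5, in what the plan calls a pilot. Finally, if the electronic record holds draw times, a time-adjusted analysis could still be done later.

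Most of this stands as a limit on size. It does not supply the missing control. Recoverable times help only if someone plans to use them, and an adjustment chosen after the results are seen is weaker than one fixed beforehand.

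A reader might infer more than the documents support:

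- **That patients are consented and drawn at all hours.** No section says so; there is only no restriction.
- **That sicker patients are drawn at different hours, for example around an emergency admission.** The study draw follows consent of a patient already in hospital, and nothing links its hour to severity.
- **That the AI groups, and so the primary result, are contaminated.** This depends on a classification rule that the plan does not define.

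**Conclusion.** The point holds in a limited form. The plan neither fixes nor analyses the time of the draw that supplies baseline cortisol and, on the natural reading, free cortisol. If draw times vary, the two free-cortisol objectives lose strength: a true correlation is multiplied by 0.89 to 0.71 for an assumed variance ratio of 0.25 to 1.0, and possibly by less reduction than that in ill inpatients. With a true correlation of 0.30 and 100 patients, power falls from 86% to between 77% and 56%.

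This rests on three assumptions: that draw times do vary, that daily variation persists in this population, and that free cortisol comes from the initial collection, which is not stated expressly. Bias needs the further condition that draw time is related to severity. The primary comparison is affected only if the AI rule uses baseline cortisol or the increment. The objectives on cholesterol esterification, HDL and spur cells against one another or against MELD and CTP are not in question here. The change is worth making because it is cheap, not because damage has been shown.

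**What to change.** 1. In Study Procedures, record the clock time of the initial collection as a study variable, taken from the electronic record.
2. In Statistical Considerations, items 2 and 5, replace the unadjusted tests for free cortisol (and for baseline cortisol, if it is analysed) with regression or partial correlation adjusted for draw time. Pre-specify a form that allows a non-linear daily pattern, such as time-of-day categories or a sine and cosine pair.
3. Where feasible without losing patients, draw the initial research sample within a common time window.
4. When the AI rule is written down, state whether it uses baseline cortisol, the increment or only the stimulated value, so that the reach of draw time into the primary comparison is known.

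Steps 1 and 2 cost one or two degrees of freedom and slightly more analysis work; they delay no one and need no extra blood. Step 3 has a real cost: some draws, and the ACTH tests that follow them, would be delayed, and a few patients might be discharged first. If that cost is too high, steps 1 and 2 alone address most of the problem.
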